8.4	RECORDING OF DATA AND RETENTION OF DOCUMENTS.....	38
8.5	AUDITING PROCEDURES	38
8.6	INSTITUTIONAL REVIEW BOARD/ETHICS COMMITTEE APPROVAL	39
8.7	PUBLICATION OF RESULTS.....	39
	APPENDIX A: SCHEDULE OF VISITS AND PARAMETERS	40
	APPENDIX B: INSTRUCTIONS FOR USE	41
	APPENDIX C: METHODS OF CLINICAL EVALUATION.....	52
9.0	REFERENCES.....	61

LIST OF ABBREVIATIONS

Abbreviation /Acronym	Term
ACD	Anterior chamber depth
AC	Anterior Chamber
ADE	Adverse device effect
AE	Adverse event
AL	Axial length
ATA	Angle to angle
BSS	Balanced salt solution
CDVA	Corrected distance visual acuity
CECC	Corneal endothelial cell count
CFR	Code of Federal Regulations
CLR	Crystalline lens rise
CRF	Case Report Form
CME	Cystoid macular edema
D	Diopters
CV	Coefficient of variation
DFE	Dilated fundus exam
DIA	Device Investigator Agreement
DOA	Delegation of Authority
ECD	Endothelial cell density
eQMS	Electronic Quality Management System
EVO Visian ICL	Brand name for VICMO and VTICMO ICL models.
EVO+ Visian ICL	Brand name for VICM5 and VTICM5 lens models.
FDA	United States Food and Drug Administration
FTP	Foam tip plunger
GCPs	Good Clinical Practices
% hex	Percent hexagonality
HEMA	Hydroxyethyl methacrylate
HPMC	Hydroxypropyl methylcellulose
ICF	Informed Consent Form
ICH	International Conference on Harmonisation
ICL	Implantable Collamer Lens
IOD	Implantation Orientation Diagram
IOL	Intraocular lens
IOP	Intraocular pressure
IRB	Institutional Review Board
ISO	International Organization for Standardization
LogMAR	Logarithm of Minimal Angle of Resolution
MICL	Visian ICL for Myopia
MRSE	Manifest refractive spherical equivalent

Abbreviation /Acronym	Term
NSAID	Non-steroidal, anti-inflammatory drug
OCOS	STAAR Visian ICL Online Calculation and Ordering Software
OCT	Optical coherence topography
PI	Principal Investigator/ Peripheral iridotomy
PMA	Premarket Approval Application
PTP	Pigment to pigment
QOL	Quality of life
QID	Four times per day
RD	Retinal detachment
SAE	Serious Adverse Event
SE	Spherical equivalent
SOP	Standard Operating Procedure
SPE	Safety and performance endpoint
STS	Sulcus to sulcus
SUN	Standardization of uveitis nomenclature
TASS	Toxic anterior segment syndrome
TMICL	Visian Toric ICL for Myopia with Astigmatism
UDVA	Uncorrected Distance Visual Acuity
US	United States
UV	Ultraviolet
VA	Visual acuity
VICM5	Model number for EVO+ Visian ICL for Myopia
VTICM5	Model number for EVO+ Visian ICL for Myopia with Astigmatism
VICMO	Model number for EVO Visian ICL for Myopia
VTICMO	Model number for EVO Visian ICL for Myopia with Astigmatism
WTW	White to white
YAG	Yttrium Aluminum Garnet

NOTE: The first occurrence of some abbreviations is not spelled out in the document (e.g., units of measure).

SYNOPSIS

STAAR Surgical Company Study #CP19-01	
Revision chronology:	Rev 2, 2020.01.30
Title:	A Multicenter Clinical Evaluation of the EVO/EVO+ Visian® Implantable Collamer® Lens
Type of study:	Prospective, open-label, multicenter.
Objective(s):	The objective of this study is to evaluate the safety, and to collect supportive data concerning the effectiveness of the EVO/EVO+ Visian® Implantable Collamer® Lens (ICL).
Study design:	This study will enroll and implant approximately 333 subjects (up to 333 primary eyes and up to an additional 333 fellow eyes) at up to 20 clinical sites in the US. Potential subjects who meet all eligibility criteria will be offered consecutive enrollment in the study and have surgery to implant study lenses in either one or both eyes. Postoperatively, subjects will return for visits at regularly scheduled intervals through Postoperative Visit 8 (1050 – 1170 days after surgery; see Appendix A). The analysis of the primary endpoints will be conducted after a minimum of 300 primary eyes complete Postoperative Visit 5 (Day 147 – 182) to support Supplement 35 to PMA P030016.
Inclusion criteria:	
 1. Subjects 21 through 45 years old at time of surgery. 2. For EVO/EVO+ ICL for Myopia: 
 • Moderate to high myopia ranging from -3.00 D to ≤ -20.00 D spherical equivalent (SE) in the spectacle plane, with less than or equal to 2.50 D of astigmatism (in the spectacle plane). 
For EVO/EVO+ Toric ICL for Myopia with Astigmatism:
 
 • Moderate to high myopic astigmatism with spherical equivalent ranging from -3.00 D to ≤ -20.00 D (in the spectacle plane) and cylinder in the range of 1.00 D to 4.00 D (in the spectacle plane). • Stable refractive history within 0.50 D cylinder for 1 year prior to implantation as determined by the Investigator. 3. Stable refractive history within 0.50 D for spherical equivalent 1 year prior to implantation as determined by the Investigator. 4. For a subject who is expected to have residual postoperative cylindrical refractive error of ≥ 1 D (as determined by STAAR Online Calculation and Ordering Software, OCOS), the subject should be given the opportunity to experience his/her vision with the anticipated correction. 5. Anterior chamber depth (ACD) 3.00 mm or greater, when measured from the corneal endothelium to the anterior surface of the crystalline lens. 6. Meet minimum endothelial cell density (ECD) requirements for age and ACD (refer to the “Minimum ECD for Age and True ACD*” table below).

STAAR Surgical Company Study #CP19-01	
	
 7. Correctable Distance Visual Acuity (CDVA) to at least 20/40 in the eye(s) to be treated; and absent of ocular pathology (except that myopic degeneration is allowed). 8. Difference between cycloplegic refraction spherical equivalent (CRSE) and manifest refraction spherical equivalent (MRSE) of < 0.75 D. 9. For current contact lens wearers, stable MRSE (within ± 0.5 D) on two consecutive examination dates with stability of the refraction determined by the following criteria: 
 – Discontinuation of contact lens use for at least 2 weeks (rigid contact lenses and all toric contact lenses) or 3 days (non-toric soft contact lenses) prior to the first refraction; – Two refractions performed at least 7 days apart. 10. Able and willing to return for scheduled follow-up examinations after surgery. 11. Subjects must be able to read, understand and provide written informed consent on the Institutional Review Board (IRB) approved Informed Consent Form (ICF) and provide authorization as appropriate for local privacy regulations.
Exclusion criteria:	
 1. Younger than 21 or older than 45 years of age. 2. With true ACD < 3.00 mm*. 3. Anterior chamber angle less than Grade III as determined by gonioscopic examination. 4. Do not meet the minimum ECD as defined in the “Minimum ECD for Age and True ACD*” table below. 5. Coefficient of variation (CV) of endothelial cell area of > 0.45. 6. Percent hexagonality (% hex) of endothelial cell shape ≤ 45 %. 7. Unstable or worsening nearsightedness. 8. Ocular hypertension or glaucoma. 9. Pseudoexfoliation. 10. Pigment dispersion. 11. History or clinical signs of iritis/uveitis. 12. Insulin-dependent diabetes or diabetic retinopathy. 13. History of previous ocular surgery. 14. Cataract of any grade. 15. Progressive sight threatening disease or other previous or current ocular conditions, other than myopia or myopic degeneration, which may predispose for future complication in either eye. 16. Serious, acute, chronic or systemic, non-ophthalmic disease or illness that would increase the operative risk, confound the outcome(s) of the study or which may preclude study completion (e.g., immunocompromised, connective tissue disease, clinically significant atopic disease, uncontrolled diabetes, etc.).

STAAR Surgical Company Study #CP19-01																													
	
17. Monocular subjects.
 
18. For EVO/EVO+ ICL for myopia: myopia less than -3.00 D or greater than -20.00 D SE (in the spectacle plane) and/or with greater than 2.50 D of astigmatism (in the spectacle plane).
 
19. For EVO/EVO+ Toric ICL for myopia with astigmatism: myopia less than -3.00 D or greater than -20.00 D SE (in the spectacle plane) and/or refractive cylinder (in the spectacle plane) less than 1.00 D and greater than 4.00 D.
 
20. Pregnant or nursing women, or those who plan to become pregnant over the course of this clinical study or has another condition with associated fluctuation of hormones that could lead to refractive changes.
 
21. Involved in another clinical study or who may have been involved in a different clinical study within 30 days prior to this clinical study or will be involved in a different clinical study while participating in this study.
 
22. Subjects who, in the judgment of the Investigator, present any emotional, physiologic, or anatomical condition which may preclude participation in this study or provide an inappropriate landscape for the intended study treatment.
 
Minimum Endothelial Cell Density for Age and True ACD*
 
  
 Age	Minimum ECD ACD ≥ 3.0 mm	Minimum ECD ACD ≥ 3.2 mm	Minimum ECD ACD ≥ 3.5 mm	
   
 21-25	3875 cells/mm²	3800 cells/mm²	3250 cells/mm²	
 
 26-30	3425 cells/mm²	3375 cells/mm²	2900 cells/mm²	
 
 31-35	3025 cells/mm²	2975 cells/mm²	2625 cells/mm²	
 
 36-40	2675 cells/mm²	2625 cells/mm²	2350 cells/mm²	
 
 41-45	2350 cells/mm²	2325 cells/mm²	2100 cells/mm²	
 
 >45	2075 cells/mm²	2050 cells/mm²	1900 cells/mm²	
  
 
*The true ACD is defined as the distance from the apex of the posterior corneal surface to the apex of the anterior crystalline lens surface. Many measuring devices provide an ACD measurement defined as the distance from the apex of the anterior corneal surface to the apex of the anterior crystalline lens surface. If the surgeon is using an instrument that measures from the anterior corneal surface, the thickness of the cornea must be subtracted to get the true ACD.
	Age	Minimum ECD ACD ≥ 3.0 mm	Minimum ECD ACD ≥ 3.2 mm	Minimum ECD ACD ≥ 3.5 mm	21-25	3875 cells/mm ²	3800 cells/mm ²	3250 cells/mm ²	26-30	3425 cells/mm ²	3375 cells/mm ²	2900 cells/mm ²	31-35	3025 cells/mm ²	2975 cells/mm ²	2625 cells/mm ²	36-40	2675 cells/mm ²	2625 cells/mm ²	2350 cells/mm ²	41-45	2350 cells/mm ²	2325 cells/mm ²	2100 cells/mm ²	>45	2075 cells/mm ²	2050 cells/mm ²	1900 cells/mm ²
Age	Minimum ECD ACD ≥ 3.0 mm	Minimum ECD ACD ≥ 3.2 mm	Minimum ECD ACD ≥ 3.5 mm																										
21-25	3875 cells/mm ²	3800 cells/mm ²	3250 cells/mm ²																										
26-30	3425 cells/mm ²	3375 cells/mm ²	2900 cells/mm ²																										
31-35	3025 cells/mm ²	2975 cells/mm ²	2625 cells/mm ²																										
36-40	2675 cells/mm ²	2625 cells/mm ²	2350 cells/mm ²																										
41-45	2350 cells/mm ²	2325 cells/mm ²	2100 cells/mm ²																										
>45	2075 cells/mm ²	2050 cells/mm ²	1900 cells/mm ²																										
Duration of Treatment	Eligible subjects who are enrolled in the study will be seen for 8 postoperative study visits over the course of approximately 3 years (1050 – 1170 days) after surgery.																												
Investigational device:	The investigational devices, EVO/EVO+ lenses, include a refractive optic and features a single piece lens design with a convex/concave optic zone of 4.9 to 6.1 mm diameter (according to model and power) and a 0.36 mm																												

STAAR Surgical Company Study #CP19-01	
	
diameter central port. The lens is manufactured from Collamer, a proprietary hydroxyethyl methacrylate (HEMA)/porcine-collagen biocompatible polymer material with an ultraviolet (UV) absorber. The lens is manufactured in four overall diameters: 12.1, 12.6, 13.2, and 13.7 mm to accommodate different eye sizes and feature a plate-haptic design with a central convex/concave optical zone and incorporate a forward vault to minimize contact with the central anterior capsule. The lens is supplied with a delivery system for implantation through an incision of 3.5 mm or less.
 
EVO/EVO+ lenses have orientation markings on the footplates to ensure they are implanted in the correct orientation. When correctly oriented the orientation markings will be on the leading right/trailing left footplates.
 
The EVO/EVO+ Toric lenses are labeled using a plus cylinder axis format and have two engraved lines, one on each side of the optic to aid with the axis alignment of the lens. The following EVO/EVO+ Models will be included in this study:
 
 • EVO/EVO+ Visian Implantable Collamer Lens for Myopia: VICMO12.1, VICMO12.6, VICMO13.2, VICMO13.7, VICM5_12.1, VICM5_12.6, VICM5_13.2, VICM5_13.7 • EVO/EVO+ Visian Toric Implantable Collamer Lens for Myopia with Astigmatism: VTICMO12.1, VTICMO12.6, VTICMO13.2, VTICMO13.7, VTICM5_12.1, VTICM5_12.6, VTICM5_13.2, VTICM5_13.7 
All study lenses will be available in -3.00 D to -16.00 D spherical equivalent dioptric powers. The EVO/EVO+ Visian Toric ICLs will also be available in cylinder dioptric power of 1.00 D to 4.00 D.

Study endpoints:	
Primary Endpoints
 
Primary endpoints will be evaluated in primary eyes only.
 
 • Incidence of peripheral iridotomy (PI) required to treat elevated intraocular pressure (IOP) caused by mechanical pupillary block through Postoperative Visit 5 (Day 147 – 182). 
The prespecified safety and performance endpoint (SPE rate) target for the first primary study endpoint is the rate of secondary PI required to treat elevated IOP caused by mechanical pupillary block with the approved and currently marketed MICTL and TMICL devices in the United States, which is approximately 0.3%.
 
The additional primary endpoints have no prespecified performance targets:
 
 • Distribution of percent ECD losses and the percent of eyes that have ECD <1500 and ECD <1000 through Postoperative Visit 5 (Day 147 – 182). • Incidence of adverse events (AEs) through Postoperative Visit 5 (Day 147 – 182). 
Secondary Endpoints
 
Secondary endpoints will be evaluated in all eyes (primary and fellow eyes) using descriptive statistics with comparisons to PMA data for the approved and currently marketed MICTL and TMICL devices, where

STAAR Surgical Company Study #CP19-01	
	
appropriate. The secondary endpoints have no prespecified performance targets.
 
 • Incidence of PI required to treat elevated IOP caused by mechanical pupillary block through Postoperative Visit 5 (Day 147 – 182). • Distribution of percent ECD losses and the percent of eyes that have ECD <1500 and ECD <1000 through Postoperative Visit 5 (Day 147 – 182). • Incidence of AEs through Postoperative Visit 5 (Day 147 – 182). 
Additional Study Parameters
 
Additional Study Parameters will be evaluated in all eyes (primary and fellow eyes). There are no prespecified performance targets for the additional study parameters.
 
 • MRSE within ± 1.00 D of target at Postoperative Visit 5 • MRSE within ± 0.50 D of target at Postoperative Visit 5 • Uncorrected distance visual acuity (UDVA) of 20/40 or better at Postoperative Visit 5 (for those eyes with CDVA 20/20 or better at Preoperative Visit) • CDVA through Postoperative Visit 8 (Day 1050 – 1170) • Distribution of percent ECD losses and the percent of eyes that have ECD <1500 and ECD <1000 through Postoperative Visit 8
Statistical methods:	
The first primary study endpoint is defined as the incidence of PI required to treat elevated IOP caused by mechanical pupillary block through Postoperative Visit 5. The primary analysis will be performed on a minimum of 300 primary eyes that have completed Postoperative Visit 5.
 
Based on complaint data, the event rate for secondary PI required to treat elevated IOP caused by mechanical pupillary block for the approved and currently marketed MICAL and TMICAL devices pupillary block is approximately 0.3%.
 
The other primary endpoints will be studied using the first treated (i.e., primary) eyes. Secondary endpoints and additional study parameters will be studied using all (primary and fellow) eyes. Data will be summarized with point estimates and exact binomial confidence intervals for binary outcomes such as MRSE within 0.50 D and 1.00 D of target and UDVA 20/40 or better. Continuous outcomes (e.g., %hex, CV) will be described with summary statistics to include N, mean, standard deviation, minimum and maximum, first and third quartiles, and median. Distributions, such as CDVA loss, trabecular pigmentation, peripheral anterior synechiae (PAS), anterior chamber (AC) cells and flare will be summarized by number and percentage for each visit.
 
ECD loss over the 1050 – 1170 days of follow up will be modeled using a bi-exponential model with adjustment for correlation between paired eyes. ECD and change in ECD will be summarized at each visit. The number and percentage of eyes with ECD < 1000 and < 1500 will be summarized over time using descriptive statistics.
 

1.0 INTRODUCTION

The Visian® ICL for myopia (model MICL) was approved by FDA (PMA P030016) in 2005. The Visian® Toric ICL for the correction/reduction of myopia with astigmatism (model TMICL) was approved by FDA (PMA Supplement P030016/S001) in 2018.

These lens models offer an intraocular alternative for the correction of refractive error in those who currently utilize spectacle and/or contact lens correction. Other alternative refractive surgical procedures include: excimer laser surgery (including photorefractive keratectomy (PRK), laser assisted in situ keratomileusis (LASIK) and small incision lenticular extraction (SMILE)), radial keratotomy (RK), automated lamellar keratectomy (ALK), epikeratoplasty, intracorneal implants (lenses or rings), anterior chamber and sulcus-placement phakic intraocular lenses (IOLs), or a combination of one or more of these procedures.

In 2011, alternate designs of the current FDA approved lenses were introduced outside of the US; the EVO Visian® Implantable Collamer® Lens for myopia (model VICMO), and EVO Visian® Toric Implantable Collamer® Lens for myopia with astigmatism (model VTICMO). These devices (EVO lenses) are largely the same as the parent devices available in the US (MICL and TMICL), with the main difference being the addition of a 0.36 mm central hole in the optic. In 2015, EVO+ lenses (models VICM5 and VTICM5 for myopia and myopia with astigmatism, respectively) were introduced outside of the US. These models include a slightly larger optic diameter than the EVO lens models to offer additional options for patients with larger pupil sizes.

The addition of the central hole to the EVO/EVO+ lens models facilitates the flow of aqueous humor through the lenses, eliminating the need for peripheral iridotomies (PIs) prior to implantation. Where these lens models are available, patients require fewer office visits and procedures prior to implant surgery, without introducing new adverse events (AEs) or increasing the occurrence of known AEs as compared to the parent devices.

The benefits of the STAAR ICL (all models) have been demonstrated by predictable, stable refractive correction¹ and a high efficacy index,² as well as improvements in quality of vision³ and quality of life (QOL).⁴ Long-term studies investigating the safety profile of the STAAR ICL have demonstrated low rates of AE.^{5,6}

2.0 OBJECTIVE

The objective of this study is to evaluate the safety, and to collect supportive data concerning effectiveness of the EVO/EVO+ Visian® Implantable Collamer® Lens (ICL).

3.0 STUDY DESIGN

3.1 Description of Study Design

This study will enroll and implant approximately 333 primary eyes and up to an additional 333 fellow eyes from subjects who qualify for bilateral implantation, at up to 20 clinical sites in the US. Postoperatively, subjects will return for visits at regularly scheduled intervals through

Postoperative Visit 8 (Day 1050 – 1170) as described in Appendix A. The analysis of the primary endpoint will be conducted after a minimum of 300 primary eyes complete Postoperative Visit 5 (Day 147 – 182) to support the Premarket Application (PMA Supplement P0930016/S035) of the investigational devices.

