6.3 Reporting

6.3.1 On-Site Expedited Reporting

The Investigator is obligated to report the following to the Sponsor within 24 hours of becoming aware of the event to ensure the safety of all participants in the study and to meet regulatory reporting requirements:

- all **SAEs**, regardless of relationship to study device or study protocol,
- all secondary surgical interventions (removal, replacement or repositioning) involving the study lens and events that cause these interventions,
- loss of CDVA ≥ 10 letters compared to the baseline (Preop Visit) at Postoperative Visit 5 (Day 147-182), or later
- all **non-serious AEs** determined to be related to the study device (ADEs)
- all device malfunctions that do not result in one of the above reportable events

When reporting these events to the Sponsor, the site should forward any supporting documents along with the appropriate reporting form and the corresponding CRF, if applicable. Refer to the Personnel and Facilities section for Sponsor contact information for reporting of SAEs/ADEs and device malfunctions. Sites must also report applicable events to the reviewing IRB per its established reporting procedures.

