7.0 STATISTICAL METHODS

7.1 Study Endpoint and Parameters

7.1.1 Primary Endpoints

Primary endpoints will be evaluated in primary eyes only.

- Incidence of PI required to treat elevated IOP caused by mechanical pupillary block through Postoperative Visit 5 (Day 147 – 182).

The prespecified safety and performance endpoint (SPE rate) for the first primary study endpoint is the rate of PI required to treat elevated IOP caused by mechanical pupillary block with the approved and currently marketed MICL and TMICL devices, which is approximately 0.3%.

The additional primary endpoints have no prespecified performance targets:

- Distribution of percent ECD losses and the percent of eyes that have ECD <1500 and ECD <1000 through Postoperative Visit 5 (Day 147 – 182).
- Incidence of AEs through Postoperative Visit 5 (Day 147 – 182).

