7.2 Sample Size

Based on complaint data, the event rate for secondary PI required to treat elevated IOP caused by mechanical pupillary block for the approved and currently marketed MICTL and TMICTL devices is approximately 0.3%. Following the recommended analysis in ISO 11979-7:2018, Annex E, for cumulative adverse events, the null hypothesis is that the true rate of PI required to treat elevated IOP caused by mechanical pupillary block is less than or equal to the SPE rate, and the alternative hypothesis is that the true rate of PI required to treat elevated IOP caused by mechanical pupillary block is greater than the SPE rate:

$$H_0 \text{ (null hypothesis): } \pi \leq 0.3\%$$

$$H_a \text{ (alternative hypothesis): } \pi > 0.3\%$$

where π is the observed rate of PI required to treat elevated IOP caused by mechanical pupillary block. Based on the analysis in ISO 11979-7:2018, Annex E, the maximum number of cases allowed before the SPE rate is exceeded for 300 primary eyes of 300 subjects is 3.

To allow for losses of 10% per year, a total of up to 333 primary eyes of up to 333 subjects will be enrolled.

In addition, in order to detect an AE with a true probability of occurrence among eyes of 1% with 95% probability, based on the binomial distribution, a sample of at least 300 eyes is required.

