7.4 Statistical Analysis

The first primary study endpoint is defined as the incidence of PI required to treat elevated IOP caused by mechanical pupillary block through Postoperative Visit 5. The primary analysis will be performed on a minimum of 300 primary eyes that have completed Postoperative Visit 5. Based on complaint data, the SPE rate for secondary PI required to treat elevated IOP caused by mechanical pupillary block is approximately 0.3% for MICTL/TMICTL. Based on the recommended analysis in ISO 11979-7:2018, Annex E, the maximum number of cases allowed before the SPE rate is exceeded for 300 primary eyes of 300 subjects is 3.

The other primary endpoints will be studied using the first treated (i.e., primary) eyes. Secondary endpoints and additional study parameters will be studied using all (primary and fellow) eyes. Data will be summarized with point estimates and exact binomial confidence intervals for binary outcomes such as MRSE within 0.50 D and 1.00 D of target and UDVA 20/40 or better. Continuous outcomes (e.g., %hex, CV) will be described with summary statistics to include N, mean, standard deviation, minimum and maximum, first and third quartiles, and median. Distributions, such as CDVA loss, trabecular pigmentation, PAS, AC cells and flare will be summarized by number and percentage for each visit.

ECD loss over the 1050 – 1170 days of follow up will be modeled using a bi-exponential model with adjustment for correlation between paired eyes. ECD and change in ECD will be summarized at each visit. The number and percentage of eyes with ECD < 1000 and < 1500 will be summarized over time using descriptive statistics.

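### The PI test may be run on 300 Visit 5 completers although about 333 primary eyes are implanted, so a PI in an implanted primary eye can fall outside the only endpoint with a target

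*Combined protocol and SAP*

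**What the plan says.** Section 3.1 plans the number of eyes as follows: "This study will enroll and implant approximately 333 primary eyes". Section 7.2 explains the excess over 300: "To allow for losses of 10% per year, a total of up to 333 primary eyes of up to 333 subjects will be enrolled".

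The trigger for the analysis (3.1) is "The analysis of the primary endpoint will be conducted after a minimum of 300 primary eyes complete Postoperative Visit 5". The analysed set (7.4) is described in similar terms: "The primary analysis will be performed on a minimum of 300 primary eyes that have completed Postoperative Visit 5". The synopsis repeats both. None of these places gives an upper number, a calendar date, a rule to wait for the remaining implanted eyes, or a database-lock rule.

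Section 7.3 defines a safety population of all eyes implanted with a study lens and rules out imputation. It does not say that this population is used for the PI test, and 7.4 describes completers instead.

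The benchmark is about 0.3%, described in 7.1.1 as "the rate of PI required to treat elevated IOP caused by mechanical pupillary block with the approved and currently marketed MICL and TMICL devices". In 7.2, "the null hypothesis is that the true rate of PI required to treat elevated IOP caused by mechanical pupillary block is less than or equal", with the benchmark as the bound, and the alternative is that it is higher. Sections 7.2 and 7.4 give a limit of 3 cases for 300 eyes and no limit for any other number.

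**The concern.** The first primary endpoint is the only one with a performance target, and its analysis supports a PMA supplement. As written, any number of completers from 300 upward satisfies the plan. Two groups of implanted primary eyes can fall outside the test: those still on their way to Visit 5 when the cut is made, and those that left before Visit 5. A PI in either group would be known and reportable, yet would not have to enter the count.

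The effect runs one way. The device passes by not exceeding 3 cases, the limit is the same at 300 and at 333 eyes, and adding eyes can add events but cannot remove them. Leaving eyes out can only make a pass easier. The rule needs no bad intent to matter: without a stated cut-off, the sponsor cannot show why the analysis fell where it did.

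**Working it through.** **Inputs.** Benchmark 0.3%, limit 3, 300 analysed and 333 enrolled eyes, 10% loss per year (7.1.1, 7.2, 7.4); Visit 5 window Day 147 to 182 (5.1). Alpha is not stated. The plan only refers to the standard: "Following the recommended analysis in ISO 11979-7:2018, Annex E, for cumulative adverse events". One-sided 0.05 is assumed here, with 0.025 as a check.

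**1. The plan's own figures.** With X binomial(300, 0.003), P(X ≥ 3) = 0.0626 and P(X ≥ 4) = 0.0133. The largest non-significant count is 3 at either alpha, so the stated limit reproduces. Enrolment: 300 / 0.9 = 333.3, against 333 stated.

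**2. The limit for more eyes.** With 333 eyes, P(X ≥ 3) = 0.0798 and P(X ≥ 4) = 0.0187, so the limit is still 3. It is 3 for every number of eyes from 274 to 456 at 0.05, and from 207 to 364 at 0.025.

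**3. An example that changes the result.** 3/300 gives p = 0.063 and passes. One further PI among the other 33 eyes gives 4/333, p = 0.019, and fails.

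**4. How many eyes are at stake.** The upper bound is 333 − 300 = 33. If losses accrue at 10% per year, the number completing Visit 5 is 333 × 0.9^(147/365) = 319 to 333 × 0.9^(182/365) = 316. So about 16 to 19 evaluable eyes could be omitted by an early cut. The rest of the 33 are early exits, which the completer wording also leaves out.

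**5. Chance of exceeding 3 cases, P(X ≥ 4).**

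| True rate | 300 eyes | 316 eyes | 319 eyes | 333 eyes |
|---|---|---|---|---|
| 0.3% | 1.3% | 1.6% | 1.6% | 1.9% |
| 0.5% | 6.5% | 7.6% | 7.8% | 8.8% |
| 1.0% | 35.3% | 38.9% | 39.5% | 42.7% |
| 1.25% | 51.7% | 55.8% | 56.5% | 59.9% |

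From unrounded values, the gain over 300 eyes at a true rate of 1% is 3.6 to 4.3 points with 316 to 319 eyes and 7.4 points with 333. At 0.3% it is 0.2 to 0.3 points and 0.5 points. Of the rates tried (0.3% to 3%), the gap between 300 and 333 eyes is largest at 1.25%, at 8.2 points.

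**6. What waiting costs.** Section 3.4 gives about 46 months in total, or 46 × 30.44 = 1,400 days. Subtracting 1,170 or 1,050 days of follow-up leaves about 230 to 350 days of recruitment. If recruitment is uniform (an assumption), the last 33 of 333 eyes trail the 300th by about 23 to 35 days, plus the visit window.

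**The case against.** A reader might infer something stronger: that in an open-label study the sponsor could watch the count, choose a favourable cut-off, and so raise the chance of passing above what was designed. The documents do not support that. The limit is constant over the whole range and the cumulative count cannot fall, so any data set that passes at a later cut also passes at the first 300 completers. No choice of date can beat the planned 300-eye analysis. The contrast of 35.3% with 42.7% is the detection available from 300 eyes against 333; it is not inflation from an informed choice. This objection stands.

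Three further objections stand in part.

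- **The extra 33 eyes are the dropout allowance.** Treating all 33 as evaluable at Visit 5 assumes no losses. On the plan's own loss rate, 16 to 19 is the fair number.
- **Events in omitted eyes do not disappear.** Section 6.1.1 requires every secondary surgical intervention to be reported as an adverse event and names iridotomy for pupillary block. Section 7.3 covers all implanted eyes. But neither section puts the event into the tested count.
- **It is an inference that the sponsor sees each PI at once.** Section 6.3.1 says "The Investigator is obligated to report the following to the Sponsor within 24 hours of becoming aware of the event", but the list that follows does not name PI, and its item on secondary surgery concerns the lens. A PI would probably arrive as a serious event, as a device-related event or through the CRF.

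The public copy lacks the front pages and one block of the synopsis' statistical methods, so a cut-off rule there cannot be excluded.

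**Conclusion.** The point holds as a loss of detection and a gap in the definition of the analysis set. The plan permits the PI test to ignore events in implanted primary eyes outside a set of at least 300 completers, and it does not reconcile 7.4 with 7.3.

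The size is modest. At a true rate of 1%, a 300-eye cut gives up about 4 points of detection against all expected completers, and 7.4 points at most against all implanted eyes. At the benchmark the effect is negligible. The 333-eye figures are an upper bound because they treat every implanted eye as fully followed. All figures assume independent primary eyes with a common rate. The limit of 3 rests on an assumed one-sided alpha of 0.05 or 0.025.

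It should still be changed. The eyes are already to be enrolled and followed, detection of a rate about three times the benchmark is only 35.3% at 300 eyes, and the correction is a matter of wording.

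**What to change.** Before enrolment starts, state in 3.1, 7.4 and the synopsis that:

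1. the governing primary analysis takes place when the last implanted primary eye has completed Visit 5, passed Day 182 or exited;
2. it counts every qualifying PI through Visit 5 in all implanted primary eyes, so that 7.4 agrees with 7.3, and reports how many eyes exited early;
3. the limit is 3 for the number of eyes analysed, with the alpha behind it stated.

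If the submission cannot wait, fix the earlier cut as the date on which the 300th primary eye completes Visit 5. Count PIs in all primary eyes implanted by then, use that number as the denominator, label the result preliminary, and state that the all-eyes analysis governs.

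The cost is a few sentences, plus either some weeks' wait or one repeat table. No visit, procedure or enrolment number changes.
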